Study Title: Accelerated Genital Tract Aging in HIV: Estradiol Clinical Trial

NCT04079218

IRB Number: 2019-10529

Accelerated genital tract aging in HIV: estradiol clinical trial

1. Background

HIV is associated with accelerated and accentuated aging as evidenced by *earlier onset* and *increased prevalence* of several age-related conditions including cardiovascular, neurocognitive and bone disease¹⁻⁴. Chronic HIV infection and aging may be linked by a common mechanism: inflammation⁵, which is fueled by ongoing low-level viral replication, microbial translocation, immunosenescence, immune activation and ART use⁶. However, the link between HIV infection and genital tract aging in women is understudied and has important clinical implications. The phenotype of female genital tract (FGT) aging is characterized by vaginal dysbiosis (increase in diverse anaerobes and decrease in acid-producing lactobacilli) and mucosal inflammation. These changes are associated with an increased risk for urinary tract and sexually transmitted infections (STI), vaginal atrophy, HIV acquisition and shedding^{7,8,9}. Among incident US HIV infections in 2015, 17% occurred in persons >50 years of age. Approximately 45% of people living with HIV in the US are aged ≥ 50 ^{10,11}, and by 2030 an estimated 70% will be over age 50, underscoring the importance of studying the effects of aging on the FGT and genital health as well as HIV acquisition and shedding.

This proposal will test the hypothesis that HIV is associated with earlier onset and more pronounced changes in the FGT characterized by vaginal dysbiosis and mucosal inflammation. I propose a cross-sectional study to compare a phenotype of FGT aging in HIV-infected (HIV+) and HIV-uninfected (HIV-) menopausal women aged 45-70 years and predict that younger HIV+ menopausal women (45-55 years) will have a phenotype similar to older (56-70 years) HIV-menopausal women. I will also explore whether topical estradiol therapy in HIV+ women with vaginal atrophy will improve symptoms and the age-related phenotype of dysbiosis and inflammation. Results of these studies have important clinical implications and could lead to recommendations for earlier and/or more aggressive treatment of vaginal atrophy in HIV+ women.

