Vaginal atrophy is common but undertreated especially in women living with HIV (WLWH). Vaginal atrophy affects up to 45% of menopausal women²¹ and presents with symptoms of vaginal dryness and dyspareunia, as well as urinary symptoms. Although the systemic vasomotor symptoms of menopause (e.g. hot flashes) often improve with time, atrophy symptoms persist. Intravaginal estrogen is effective for the treatment of vaginal atrophy with a favorable safety profile^{22-25,26-29} compared to systemic preparations. However, it is estimated that only 25% of symptomatic women seek medical attention²¹ and even in these women it is undertreated. With the increased availability of antiretroviral therapy (ART) and associated aging of the HIV population^{30,31}, large numbers of WLWH will enter menopause, placing them at risk for vaginal atrophy. Topical estrogen therapy has not been studied in WLWH, despite the findings that they experience and report menopausal symptoms at an earlier age than HIV- women³²⁻³⁵. Moreover, severe menopausal symptoms have been associated with reduced adherence to ART placing menopausal WLWH at risk for possible drug resistance and adverse HIV related health outcomes³⁶. Low dose intravaginal estrogen (Vagifem 10 µg) is safe, effective and FDA approved for the treatment of symptomatic vaginal atrophy. Because of low systemic absorption (3-11 pg/ml)^{37,38}, there is little risk of complications nor need for progesterone supplementation^{22,23,39}. The boxed warning for risk for endometrial cancer and cardiovascular disease (CVD) is based on extrapolations of data from clinical trials of systemic hormonal therapy, with substantially higher levels of exposure. There is no randomized trial or consistent observational evidence linking low-dose vaginal estrogen to cancer, CVD, dementia, or thromboembolism. A Working Group on Women's Health and Well-Being in Menopause has proposed to the FDA a labeling change⁴⁰.

2. Innovation

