This is the first study specifically designed to test an intervention to restore local estrogen in HIV+ menopausal women with the goal of improving symptoms of atrophy, promoting an optimal vaginal microbiome and reducing GT inflammation. Previous studies have demonstrated a reduction in symptoms of vaginal atrophy and increased lactobacilli after oral estrogen replacement in HIV- menopausal women⁴¹. However, the effect of topical estradiol on the vaginal microbiome has not been studied nor has local estradiol treatment been systematically assessed in HIV+ women with vaginal atrophy. We will fill this research gap in this pilot randomized clinical trial. In addition to assessing improvement in clinical symptoms, we will explore the effects of topical estradiol on the vaginal microbiome, markers of mucosal inflammation, and HIV shedding.

Despite numerous studies documenting the composition of the vaginal microbiome in various disease states, our understanding of the functional relationship between the vaginal microbiome and mucosal health is limited. In order to fill this knowledge gap, we will evaluate the vaginal microbiome with Illumina MiSeq and quantitative PCR for select bacteria, and also propose to apply a **more novel technique of Ig-SEQ, which combines flow cytometry-based bacterial cell sorting and 16S sequencing to identify subpopulations of IgA and/or IgG coated bacteria, with the goal of understanding the link between bacterial species,**

mucosal inflammation and genital tract aging. We hypothesize that functional consequences of differences in the microbiome may link to immunoglobulin (Ig) coating.

3. Approach

We propose to test the hypothesis that menopausal women living with HIV (WLWH) develop genital tract aging earlier than HIV- menopausal women and that the magnitude of changes in microbiome and mucosal inflammation will be greater in HIV+ versus HIV- women. We will also test whether vaginal estradiol treatment in menopausal WLWH with vaginal atrophy will result in improvement of symptoms and an increase in Ig-coated, lactobacillus-dominant vaginal microbiota and reduction in mucosal inflammation. If the hypothesis is supported by this pilot interventional study, results would provide the foundation for a future study to evaluate the efficacy of earlier use of topical estradiol and generate new testable hypotheses to link aging, the vaginal microbiome and host mucosal immunity to HIV care.

4. Objectives and Study Design

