estradiol will improve vaginal symptoms and modify the genital tract aging phenotype. HIV+ women who agree to participate in the trial will have 3 additional study visits: randomization (Visit 3), 6 weeks after randomization (Visit 4) and 12 weeks after randomization (Visit 5). HIV- women can only participate in Aim 1 and will have 2 study visits. HIV+ women can elect to participate in Aim 1 and/or Aim 2 (2 study visits if only Aim 1 is completed; 4 study visits if only Aim 2 is completed; 5 visits if both Aims 1 and 2 are completed).

Inclusion criteria for Aim 1 (first 2 study visits):

- HIV infection or HIV negative
- Females aged 45-70
- Menopause defined by having no menstrual periods for 12 consecutive months, confirmed with serum follicle-stimulating hormone (FSH) level >40 IU/ml and serum estradiol level <20 pg/ml

In the second part of the study (Aim 2), we propose a pilot randomized clinical trial nested in the Bronx WIHS in 50 menopausal WLWH with symptomatic vaginal atrophy to assess the impact of 12 weeks of a topical low-dose estradiol vaginal tablet (Vagifem® 10 µg) on symptoms of atrophy and measures of the vaginal microbiome. Participants will be randomized 1:1 to estradiol (n=25) or no therapy (n=25) and will be followed for 12 weeks. The dosing of Vagifem® will be 1 tablet inserted using a plastic applicator (similar to a tampon) in the vagina daily for 2 weeks followed by 1 tablet inserted twice weekly (i.e., Tuesday and Friday). If we find benefit among women assigned to the estradiol arm, participants randomized to the no therapy arm will be offered vaginal estradiol treatment at the end of the study by their primary care doctor. If participants assigned to Vagifem are symptomatic beyond the 12-week study period and wish to continue Vagifem®, it can be prescribed by their primary care physician. Women will have 3 visits before (Visits 1, 2 and 3) and 2 visits following Vagifem® treatment (Visits 4 and 5). Adherence to Vagifem will be assessed with the use of participant diaries of Vagifem use and counting of used Vagifem applicators.

Inclusion criteria for Aim 2 (randomized clinical trial for HIV+ participants only):

- HIV infection
- Females aged 45-70
- Menopause defined by having no menstrual periods for 12 consecutive months, confirmed with serum follicle-stimulating hormone (FSH) level >40 IU/ml and serum estradiol level <20 pg/ml

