Women with HIV infection experience menopausal symptoms at an earlier age and are more likely to report symptoms compared to women who do not have HIV. Participants may benefit from study participation because the use of low dose topical estradiol, which has been FDA approved since 2009 for the treatment of vaginal atrophy in menopausal women, may relieve symptoms of vaginal dryness, itching, soreness, pain and urinary symptoms in women with HIV. Participants and others may benefit in the future from information learned from this study. Specifically, if we find that HIV accelerates genital tract aging, this may prompt recommendations for earlier treatment of vaginal atrophy in menopausal women with HIV.

10. Data analysis and sample size:

Aim 1: The primary exposure variables are HIV infection and age. The primary outcome is the vaginal microbiome, specifically the relative abundance and quantities of lactobacillus species as measured by illumina MiSeq and qPCR respectively. Secondary outcomes are relative abundance and quantities of specific BV associated bacteria and quantities of CVL cytokine/chemokines. Exploratory outcomes are quantities and composition of Ig coated bacteria and levels of HIV-1 in the genital tract. Multivariate linear regression will be applied for our analysis. General form of the linear regression model will be: $y_i = \mu + \beta_{age_i} + \gamma_{HIV_i} + \theta_{age_i \times HIV_i} + \delta_i \text{Covariates}_i + \dots + \epsilon_i$, in which y_i is the outcome variables subject to necessary transformation as necessary. Age will be analyzed as a continuous variable to examine the slope or rate of change in lactobacillus and as

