a dichotomous variable (e.g. age 45-55 vs. 56-70) to examine the magnitude of difference between younger and older HIV+ and HIV- menopausal participants. We have chosen the age cut offs above given the significant differences observed in the taxonomic composition of the microbiome in pilot studies when comparing HIV+ menopausal participants in these age ranges and the distribution of eligible participants in WIHS. We will adjust the regression analysis for important covariates including years since menopause, time since HIV diagnosis, HIV plasma viral load, CD4 count, ART use, and HSV-2 serostatus. Both raw p values and the false discovery rate (FDR) according to Benjamini and Hochberg will be examined. To limit the false positive rate in our analysis of secondary outcomes, an arbitrary cutoff of 0.05 for FDR will be used.

Power Considerations: We estimated the power of the proposed study using software PASS (Power and Sample Size Analysis, version 11). Given the sample size of 50 HIV- and 50 HIV+ menopausal participants, we will have >80% power for the minimal detectable difference of 0.6SD and 0.9SD between HIV (or age) group with the significance level of 0.05 and 0.0005 (a conservative Bonferroni correction for 100 independent tests). Data from preliminary studies in our lab investigating the impact of menopause and HIV status on the vaginal microbiome indicated 51 HIV+ menopausal participants had a significantly lower relative abundance of lactobacillus species of 7.3% compared to 23% for 19 HIV- menopausal participants, equivalent to about 0.8SD change. Further when comparing upper and lower age ranges of HIV+ menopausal participants, HIV+ participants age 56-70 (n=28) had significantly lower relative proportions of *L. iners* 7.4% compared to 44.7% in HIV+ menopausal participants aged 47-55.9 (n=23), equivalent to about 1.2SD change. Based on the preliminary data, we are confident that this study will have excellent power to detect effects of age and HIV.

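### Adjusting the Aim 1 model for years since menopause leaves an age coefficient that is only part of the age slope the plan sets out to examine, and a much less precise one

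*Combined protocol and SAP*

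**What the plan says.** All references are to the combined protocol and SAP.

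- Section 10, Aim 1, on exposures: "The primary exposure variables are HIV infection and age". The regression has terms for age, HIV, their product and covariates.
- Section 10, Aim 1, on the age term: "Age will be analyzed as a continuous variable to examine the slope or rate of change in lactobacillus". Age is also to be split at 45–55 versus 56–70 to give the size of the difference between younger and older women.
- Section 10, Aim 1, on covariates: "We will adjust the regression analysis for important covariates including years since menopause", followed by duration of diagnosed HIV, viral load, CD4 count, ART and HSV-2 serostatus. The only reason given is that these covariates are important.
- Section 3 gives the hypothesis that "menopausal women living with HIV (WLWH) develop genital tract aging earlier than HIV- menopausal women". Section 1 sharpens it, where the investigators "predict that younger HIV+ menopausal women (45-55 years) will have a phenotype similar to older (56-70 years) HIV-menopausal women".
- Section 4 restricts entry to menopausal women: "Menopause defined by having no menstrual periods for 12 consecutive months", with hormone confirmation. HIV groups are frequency matched on age, race and ethnicity, but not on time since menopause.

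The documents describe no Aim 1 model without years since menopause, no mediation or direct-effect target, and no sensitivity analysis on this covariate.

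**The concern.** Every participant is menopausal, so years since menopause (YSM below) is current age minus age at menopause. It is a component of the age exposure and not a separate background characteristic. Section 1 itself links dysbiosis and atrophy to the estrogen-deficient state of menopause, so time spent in that state is a plausible route by which age acts. Holding YSM fixed takes that route out of the age coefficient. Because YSM and age are also strongly correlated, whatever remains is estimated poorly.

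The planned analysis therefore does not deliver the quantity Section 10 names, the change in lactobacilli with age. A weak or null adjusted age term could be read as no age-related change when it partly reflects the covariate. The Aim 1 power statement covers age-group as well as HIV comparisons and makes no allowance for this.

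**Working it through.** **1. The plan's own power figure.** Inputs from Section 10: 50 versus 50, differences of 0.6 and 0.9 SD, significance levels 0.05 and 0.0005. Two-sided testing is assumed. With z = difference × √(50/2):

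- 0.6 × 5 = 3.0; 3.0 − 1.96 = 1.04; power 85.1% (84.4% with the t distribution).
- 0.9 × 5 = 4.5; 4.5 − 3.48 = 1.02; power 84.6% (81.1% with t).

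The claim of more than 80% reproduces, but as a plain two-group comparison with no covariates. For age it also needs an even split across the age bands, which is assumed below.

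**2. What the coefficients mean.** Write AM for age at menopause, so YSM = age − AM. Then

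b_age × age + b_ysm × YSM = (b_age + b_ysm) × age − b_ysm × AM.

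At fixed AM, the total age slope is b_age + b_ysm. With YSM in the model, the age coefficient is b_age alone.

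**3. Assumptions (none is given in the documents).** AM has mean 50 and SD 3 to 4.5, with menopause at least one year before current age. HIV brings menopause forward by 0 to 2 years. The total age effect is −0.06 SD per year, residual SD is 1, and there are 25 women in each of the four age-by-HIV cells. The age × HIV term is in the model; the other covariates are left out.

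**4. Precision of continuous age.** Over a slightly wider range (SD of AM 3 to 5, HIV shift 0 to 3 years), the age–YSM correlation is 0.77–0.90 and the variance inflation for age is 2.5–5.6. That multiplies the standard error by √2.5 = 1.6 to √5.6 = 2.4. Within the assumptions of step 3 the simulated multiplier is about 1.8–2.4.

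**5. Power for continuous age, two-sided 0.05 (simulated).**

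| Share of age effect through YSM | Without YSM | With YSM |
|---|---|---|
| None | about 99% | 50–68% |
| Half | about 98% | 15–21% |
| All | about 89–90% | about 6% (the false-positive rate, since b_age = 0) |

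Hand check of the first row. With ages uniform within 45–55 and 56–70, the variance of age is the mean of 10²/12 and 14²/12, plus (13/2)² between bands: 12.3 + 42.25 = 54.6, so SD 7.4. The standard error without YSM is 1/(7.4 × √100) = 0.0135, z = 0.06/0.0135 = 4.4, and power is about 99%. Multiplying the standard error by 1.8 gives z = 2.46 and power 69%; by 2.4, z = 1.85 and power 46%. Runs without the interaction term gave 45–71%. The ends of the range are therefore approximate, but the size of the loss is not in doubt.

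**6. The dichotomous contrast.** The band midpoints are 50 and 63, so the expected difference is 13 × −0.06 = −0.78 SD. With YSM added, and YSM having no effect of its own, the estimate falls to between −0.38 and −0.52 SD, or 49% to 67% of its value. The cause is that a two-level age variable leaves age variation within each band, and YSM, being correlated with that variation, absorbs part of the age effect. Mean YSM is about 4–7 years in the younger cells and 13–17 in the older ones, so a comparison at equal YSM also has little overlap to rest on.

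**7. HIV and interaction terms.** If HIV brings menopause forward, the adjusted HIV coefficient loses b_ysm × the HIV difference in YSM at a given age. For shifts of 1 to 3 years that difference is about 0.7 to 2.6 years. The loss is then 0.03 × 0.7 = 0.02 SD (half of the effect through YSM) to 0.06 × 2.6 ≈ 0.15 SD (all of it), and zero if there is no shift. The age × HIV coefficient changes by at most 0.005 SD per year when the YSM slope is the same in both HIV groups.

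**The case against.** The best defence is that the adjustment is deliberate and answers a sensible question. Section 1 proposes inflammation as the mechanism linking HIV and aging, and the groups are not matched on YSM. Without the covariate, an HIV difference could reflect longer estrogen deprivation. An effect net of menopausal duration is a legitimate target, and the age × HIV term, the direct test of a faster rate of change, is barely altered. All of this stands. It justifies keeping the adjusted model in the plan, but not having it as the only model when the stated aim for the age term is the slope with age.

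A reader might infer that, because YSM is age minus age at menopause, the adjusted coefficient no longer measures aging at all. That goes too far. At fixed YSM, age and age at menopause rise together. If age at menopause has no effect of its own, the coefficient is the effect of chronological age net of time since menopause. It is zero only if the whole age effect runs through YSM, and unbiased (continuous age) if none does.

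A reader might also infer that the adjustment erases a substantial HIV effect acting through earlier menopause. The documents do not support that. Section 1 says of women with HIV that "they experience and report menopausal symptoms at an earlier age than HIV- women", which concerns symptoms and not the date of menopause. No statement in the text says menopause itself comes earlier; only the title of a cited reference touches on it.

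**Conclusion.** The concern holds for the age effect. The plan names the change in lactobacilli with age, and the younger-versus-older difference, as what the age term examines, then adds a covariate that removes part of that quantity and inflates the standard error of the rest. The loss does not depend on mediation: even if YSM has no effect, continuous-age power falls to about half to two-thirds, and the dichotomous contrast loses a third to a half of its size. The stated power for 0.6 SD between age groups therefore applies only to a comparison without YSM.

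The HIV consequence is secondary: about 0 to 0.15 SD against a planned detectable difference of 0.6 SD, and conditional on earlier menopause. The conclusion about the interaction term requires a common YSM slope in the two HIV groups.

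The direction follows from the algebra and from the correlation between age and YSM. The sizes rest on the assumed distribution of age at menopause, HIV shift and age effect. The sponsor can replace these with cohort data.

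**What to change.** In Section 10, Aim 1, state that the primary targets are the total age and HIV effects, and make the model without years since menopause primary for both the continuous and the dichotomous age analyses. Keep the model with years since menopause as a named secondary analysis of effects net of menopausal duration. State that the Aim 1 power figure for age groups refers to the model without it.

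The cost is SAP wording; both models use the same data. The downside is that the primary model does not separate chronological age from duration of estrogen deprivation. The secondary model addresses that, with the limited precision shown above.

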The study is nested in Bronx WIHS, which is an NIH-funded prospective observational cohort study of HIV+ and at-risk HIV- women. We have identified 90 HIV- and 248 HIV+ Bronx and Brooklyn WIHS participants who are potentially eligible for this study. Potential participants will be invited to discuss this study at semiannual Core WIHS visits. We will recruit participants from the Bronx and Brooklyn WIHS for this study. Bronx WIHS staff will call potentially eligible participants and schedule them to come in to the Clinical Research Center at the Albert Einstein College of Medicine or the Bronx WIHS site for a screening visit. As we have done for prior studies, Brooklyn WIHS participants who are interested in participating in the study, will be contacted by the Bronx WIHS staff and seen at the Bronx WIHS site for all visits. Additional participants may be recruited

from Montefiore Medical center, and may be identified using the Center for AIDS Research Clinical Database.

6. Study procedures

Study visits will occur at the Einstein Clinical Research Center or the Bronx WIHS clinical study site. The study clinicians or study coordinator will screen participants for eligibility, discuss the study, answer any questions, and obtain written informed consent. At each scheduled research visit, a pelvic examination will be performed for the collection of the following specimens: vaginal swabs for pH, and microbiome studies; CVL; vaginal swabs to assess for infection (Visits 1 and 2 only) and vaginal biopsies and a vaginal scraping (VMI) to assess for vaginal aging at (Visits 2 and 5 only) (**Table 1**). If candida, BV, or trichomonas is diagnosed, participants will be notified and referred to their primary doctor for treatment prior to enrollment in the study. After treatment, participants may return for repeat testing and if the infection has resolved, they may be enrolled in the study.

At Visit 2 blood will be collected for estradiol and follicular stimulating hormone (FSH) levels, aging biomarkers and future studies and for HIV positive participants, CD4 and HIV-1 RNA. At Visit 5, blood will be collected for aging biomarkers and future studies. Participants will be asked at Visits 2-5 to complete a questionnaire about the presence and severity of the most bothersome symptom of atrophy, defined as vulvovaginal itching, pain, dryness, irritation or pain with penetration (dyspareunia)⁴³.

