	Visit 1 Screening	Visit 2 2 nd visit and/or Screening for Trial	Visit 3 Randomized Estradiol vs. No therapy	Visit 4 6 weeks Estradiol vs. No therapy	Visit 5 12 weeks Estradiol vs. No therapy	Safety Call 2, 8, 13 weeks
Eligibility/Informed consent	X	X	X			
Randomization to Estradiol vs. No treatment			X			
WIHS database extraction Demographics, CD4 count, plasma HIV-1 RNA, ART regimen and reported adherence, etc.	X	X				
Vaginal atrophy symptom questionnaire		X	X	X	X	X
Adverse event assessment	X	X	X	X	X	X
Vaginal swabs (n=4-5 per visit) pH, microbiome studies	X	X	X	X	X	
Cervicovaginal lavage (CVL) supernatant Immune mediators, HIV-1 RNA, RSID, saline/KOH, glycogen	X	X	X	X	X	
CVL cell pellet Nugent score, additional microbiome	X	X	X	X	X	
Wet mount (candida, trichomonas, bacterial vaginosis)	X	X				
Vaginal biopsies (2) RNA seq, future immunohistochemistry studies		X			X	
Blood collection Estradiol/FSH levels, HIV-1 RNA, CD4, plasma for future aging biomarkers		X			X	
Clinical Exam to assess for Vaginal Atrophy (VMI)		X			X	

ART=antiretroviral therapy; RSID=rapid semen identification; FSH=follicle stimulating hormone; VMI=vaginal maturation index

7. Potential Risks:

There is a small risk of bruising, blood clots or infection from blood draws. Sometimes the area of needle insertion becomes sore or red. A woman may experience mild discomfort at the time of speculum placement and sample collection. There is a very small risk of injury to the lining of the vagina from the speculum or from the vaginal scraping. There is no discomfort or risk to placement or removal of sterile saline into the vaginal area. There is no risk to CVL or vaginal swab collection. Women may experience a sharp pinch or have pain when vaginal biopsies are performed. In order to minimize the pain and discomfort of the biopsy, we will apply a topical numbing medication (benzocaine gel) to the tissue. There may be stinging, burning, redness, or itching associated with local anesthesia (topical benzocaine gel) which is rare. Biopsies may cause light bleeding. Rarely, a biopsy can cause infection and/or prolonged bleeding. Sometimes a medication is needed to stop the bleeding, which would be applied directly to the

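### The Aim 1 regression adjusts for HIV-only covariates without a rule for HIV- women: left missing, they remove the whole HIV- group; set to zero, they change what the raw HIV coefficient means

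*Combined protocol and SAP*

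**What the plan says.** Section 10, Aim 1, states: "The primary exposure variables are HIV infection and age". It then gives a single model, introduced by "General form of the linear regression model will be", with terms for age, HIV, age x HIV and covariates. Age is to be analysed both as a continuous and as a two-group variable.

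On adjustment the same section says "We will adjust the regression analysis for important covariates", and the list is "important covariates including years since menopause, time since HIV diagnosis, HIV plasma viral load, CD4 count, ART use, and HSV-2 serostatus".

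The Aim 1 power paragraph, for 50 women per group, says "we will have >80% power for the minimal detectable difference of 0.6SD and 0.9SD between HIV (or age) group", at significance levels 0.05 and 0.0005 respectively.

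On who has the measurements, the text of Section 6 describes the Visit 2 blood draw and specifies "for HIV positive participants, CD4 and HIV-1 RNA". Table 1 lists items without splitting by HIV status: "Demographics, CD4 count, plasma HIV-1 RNA, ART regimen and reported adherence, etc" for the WIHS extraction and "Estradiol/FSH levels, HIV-1 RNA, CD4, plasma for future aging biomarkers" for blood.

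No section gives a value for the HIV-only covariates in HIV- women, confines them to an HIV+ analysis, centres them, or states how missing values are handled.

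**The concern.** HIV is one of the two primary exposures, and the model must contain both groups to estimate its effect. Three of the listed covariates have no ordinary value in half the sample. Time since diagnosis does not exist for an HIV- woman; viral load and ART use can only be zero. CD4 exists in everyone but is planned only for HIV+ women.

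An analyst following the text must therefore improvise, and the obvious choices give different HIV coefficients. One choice leaves no HIV comparison. Another yields a coefficient for a kind of woman whom Aim 1 is not about, with a much larger standard error. If that coefficient were read as the adjusted HIV effect, a real difference could be reported as having disappeared after adjustment.

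**Working it through.** **1. The plan's own figure.** Two groups of 50, SD 1, two-sided (sidedness is not stated). SE = sqrt(1/50 + 1/50) = 0.20, so a 0.6 SD difference has noncentrality 0.6/0.20 = 3.0. The noncentral t with 98 df gives power 84.4% at 0.05. For 0.9 SD at 0.0005 it gives 81.1%. Both exceed 80%, so the statement reproduces for an unadjusted comparison.

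**2. Left missing.** Time since diagnosis is missing for every HIV- woman, so a complete-case fit keeps 50 of 100 women and 0 of 50 HIV- women. HIV is then constant, and neither HIV nor age x HIV can be estimated. This needs no assumption.

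**3. Set to zero: what the coefficient means.** Write m_k for the HIV+ mean of covariate k and g_k for its slope. Then

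raw HIV coefficient = (HIV contrast at HIV+ means) - sum of g_k m_k.

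The raw coefficient is the contrast at 0 years, viral-load code 0 (1 copy/mL if log10 is used) and no ART. If a whole -0.6 SD difference ran through duration, at -0.03 SD per year x 20 years, the raw coefficient would be expected at 0; simulation gave -0.01. If every HIV+ woman is on ART, the ART and HIV columns coincide and the model is singular. The chance of that is 0.95^50 = 8% at 95% use and 0.98^50 = 36% at 98% use.

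**4. Set to zero: precision.** The documents give no covariate distributions, so these inputs are assumed. Base case for HIV+ women: 18 years since diagnosis (SD 6), 95% on ART, 80% suppressed, CD4 600 (SD 250).

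A hand approximation, treating covariates as uncorrelated, adds m_k^2/(50 x variance_k) to the squared SE:
- years: (18/6)^2/50 = 0.18
- ART: 0.95^2/(50 x 0.95 x 0.05) = 0.38
- total: 0.04 + 0.18 + 0.38 = 0.60, so SE is about 0.77 before viral load is added.

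Simulated designs (residual SD 1, age centred, true HIV difference 0.6 SD) agree:

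| HIV estimate | SE (SD units) | Power |
|---|---|---|
| HIV, age, age x HIV only | 0.20 | 84% |
| Raw coefficient; years, viral load, ART zero-filled; base case | 0.81-0.87 | 11-12% |
| Same, CD4 zero-filled as well | 0.90-0.96 | about 10% |
| Most favourable of 432 input sets (10 years, SD 8; 80% on ART; no CD4) | 0.42 | 29% |
| Least favourable (22 years, SD 5; 98% on ART; CD4 zero-filled) | 1.29 | 8% |
| Contrast at HIV+ means, same fits | 0.20 | 84% |

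The last row excludes fits with CD4 measured in both groups (assumed means 600 and 900); there the contrast has SE 0.23 and power 72-73%.

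With other inputs (20 years, SD 5; 80% or 90% on ART), and with years since menopause and HSV-2 also in the model, the raw coefficient has SE 0.85-0.93 and power 11-13%. Dropping the HIV-only covariates from that model gives SE 0.20 and power 82-84%.

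**5. Same fit, different coefficient.** In one simulated dataset, zero-filling and centring at the HIV+ mean both gave R-squared 0.182. The HIV coefficient was 1.10 (SE 1.08) under the first and -0.78 (SE 0.21) under the second.

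**6. Age x HIV.** Under zero-filling, its SE per year goes from 0.0267 to 0.0269-0.0277, or 0.0286 if years since diagnosis correlates 0.4 with age.

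**The case against.** The text can be read more softly. The model is a general form, and the covariate list is introduced as non-exhaustive, so it might be a pool of candidates. That is fair as far as it goes, but the plan says the regression will be adjusted, names one model for all women, and nowhere restricts the HIV-only items.

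Four stronger readings are tempting and are not supported:

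- **That Aim 1 cannot deliver the HIV comparison.** The complete-case failure would be obvious, because the software would return no HIV estimate. The gap is visible from the covariate list alone, so a rule can be set before any outcome is seen.
- **That zero-filling destroys information.** It does not; the contrast at HIV+ means keeps its precision. Harm requires the raw coefficient to be misread. The same trap exists without any HIV covariate: with uncentred age, the HIV coefficient refers to age 0 and has SE about 1.54.
- **That the power statement is wrong.** It is correct for the unadjusted two-group difference.
- **That the documents contradict each other on CD4.** Section 6 is specific to HIV+ women. Section 4 and Table 1 are condensed lists that also name plasma HIV RNA and, in the extraction row, ART regimen, which do not apply to HIV- women. The specific statement can be read as governing.

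It is also true that the 'earlier' part of Objective A rests largely on age x HIV, which zero-filling leaves almost unchanged.

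**Conclusion.** The point holds and is worth fixing before analysis. Followed as written, the Aim 1 adjustment either removes all 50 HIV- women or produces a raw HIV coefficient that does not answer Objective A.

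The 0 of 50 count and the meaning of the zero-filled coefficient follow from the plan alone. The size of the precision loss (SE about 0.4 to 1.3 SD against 0.20; power about 8 to 29% against 84%) rests on assumed durations, ART use and viral suppression. It illustrates the problem and does not measure it in this cohort.

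The damage is confined to how the Aim 1 HIV main effect is estimated and read, plus age x HIV if HIV- women are dropped. Aim 2's randomised comparison is untouched.

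**What to change.** For the primary HIV and age x HIV estimates, fit all women with age centred (or age group coded -0.5/+0.5) and only covariates defined in both groups, for example years since menopause, HSV-2 serostatus, race and ethnicity. Put time since diagnosis, viral load, ART use and CD4 in a secondary model in the 50 HIV+ women.

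Alternatively, keep one model and enter time since diagnosis, viral load and ART use centred at the HIV+ mean, with 0 for HIV- women. The HIV coefficient is then the contrast at HIV+ mean covariates, with SE about 0.20 SD. It is the same fit as zero-filling, so it still fails if every HIV+ woman is on ART; ART use would then have to be left out.

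The cost is one paragraph of analysis text and one extra HIV+-only model. No new data are needed.
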